**Figure 3: (-)-Epicatechin metabolite profile in plasma**

**A.** (-)-Epicatechin metabolite profile in plasma 2 hours after ingestion of 1.8 mg/kg body weight (-)-epicatechin [19]. Unmodified (-)-epicatechin represented <0.5%. **B.** Profile of (-)-epicatechin metabolites in plasma after ingestion of 100g of dark chocolate (79 mg (-)-epicatechin) [47]. Data are expressed as the percentage of total plasma AUC0-24 h. Unmodified (-)-epicatechin not detected. EC-3'-Gluc, (-)-epicatechin-3'-β-D-glucuronide; EC-4'-Gluc, (-)-epicatechin-4'-β-D-glucuronide; EC-7-Gluc, (-)-epicatechin-7-β-D-glucuronide; EC-3'-S, (-)-epicatechin-3'-sulfate; 3'Me-EC-5-S, 3'-O-methyl(-)-epicatechin 5-sulfate; 3'Me-EC-4'-S, 3'-O-methyl(-)-epicatechin 4'-sulfate; 3'Me-EC-7-S, 3'-O-methyl(-)-epicatechin 7-sulfate; and 4'Me-EC-5-S, 4'-O-methyl(-)-epicatechin 5-sulfate.

The  $T_{max}$  (time to maximum plasma concentration) of (-)-epicatechin and most of its metabolites is 1-2 hours, elimination half-time ( $t_{1/2}$ ) from plasma is ~2-2.5 hours, and over 90% of the urinary excretion of these compounds was complete by 8 hours [17, 19, 21].

Oral bioavailability (peak plasma concentration/mg ingested) for (-)-epicatechin in cocoa/chocolate is ~10-20 nM/mg ingested (Table 2). Assuming ~3L plasma in a 75 kg man [51], oral bioavailability of (-)-epicatechin (% ingested dose in plasma at  $C_{max}$ , total epicatechin and metabolites), can be estimated as 1-2%. A value of 1.1% was reported for a 45 mg (-)-epicatechin dose in a green tea catechin mixture [17].

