**Figure 1: Chemical structures of flavonoid families and (-)-Epicatechin**

The majority of studies of (-)-epicatechin have utilized flavanol-rich cocoa preparations or concentrated tea extracts. Common commercial products that contain 60-90% cocoa can provide a total of ~12 mg of flavanols (monomers and multimers)/gram of chocolate. For example, 60% cocoa chocolate by Hershey will provide 0.84 mg/gram of (-)-epicatechin and 10.6 mg/gram of total flavanols (9.8 mg as multimers). (-)-Epicatechin, monomeric, isolated from tea, will be supplied by Cardero Therapeutics in gelatin capsules, each containing 25 mg (-)-epicatechin combined with excipients.

**Therapeutic Activities** Recent studies by scientists at the University of California, San Diego (UCSD) have suggested that (-)-epicatechin could reverse progressive muscle loss associated with aging and muscular dystrophy through stimulation of muscle-promoting proteins and mitochondrial biogenesis, and reduction in tissue oxidative stress, inflammation and fibrosis [4-7]. A detailed description of published and unpublished preclinical and clinical data supporting the evaluation of (-)-epicatechin in BMD is presented in Sections 5 and 6.

It must be stressed that these muscle-related therapeutic activities are unique to (-)-epicatechin and do not represent general flavonoid properties, as other flavonoids such as quercetin fail to exert similar effects. (-)-Epicatechin biology is chirally specific, as its diastereomer, catechin, is not only inactive in stimulating mitochondrial biogenesis, it antagonizes (-)-epicatechin's effects, possibly due to steric competition at a binding site. Nor is the effect due to anti-oxidation, as catechin and quercetin are anti-oxidants equal in potency to (-)-epicatechin but are inactive with respect to mitochondria.

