**Table 2: Selected human oral bioavailability studies of (-)-epicatechin**

Reference	Test Article	(-)-Epicatechin (mg)	Peak (-)-Epicatechin Species in Plasma (nM)	Peak (-)-Epicatechin Exposure (nM/mg)
Loke, W.M., et al., 2008 [52]	(-)-Epicatechin	200	3570	17.85
Ottaviani, J.I., et al., 2011 [18]	(-)-epicatechin added to cocoa vehicle	125 (mean)	~900	~7.2
Ottaviani, J.I., et al., 2012 [19]	Cocoa drink	135 (mean)	1245	9.3
Actis-Goretta, L., et al., 2012 [47]	Dark Chocolate	79	873	11.1
Donovan, J.L., et al., 2006 [53]	Cocoa drink	55	630	11.5
Schroeter, H., et al., 2006 [11]	Cocoa flavanols: 917 mg	174	~1950	~11.2
Baba, S., et al., 2000 [15]	Dark chocolate	220	4770	21.7

Oral doses of (-)-epicatechin between 25 and 200 mg have been shown to be pharmacologically relevant. A 200 mg oral dose increased measures of plasma NO and decreased the vasoconstrictor endothelin-1 [52], while administration of an ~75 mg dose (1 mg/kg body weight) resulted in significant improvement in vascular function (FMD) [11]. A recent meta-analysis of clinical data reported that an intake of 25 mg (-)-epicatechin per day was associated with significant reductions in SBP and DBP [54].

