## 5.2 POC Clinical Study #2: Age-Related Changes in Muscle Regulatory Proteins and Effect of (-)-Epicatechin on Muscle Function and Proteins in Healthy Volunteers (UCSD)

A two part study was conducted to evaluate age-related muscle changes and the effects of (-)-epicatechin on those changes (manuscript submitted for publication, 2012). In the first part, tissue bank SkM samples were obtained from young ( $28.5 \pm 7$  years,  $n=6$ ) and old ( $62 \pm 2$  years,  $n=6$ ) subjects and analyzed for the amounts of muscle regulatory proteins. Levels of SkM growth (myostatin, follistatin), differentiation (myogenin, MyoD, MEF2A, Myf5) and senescence (senescence-associated  $\beta$ -galactosidase: SA- $\beta$ -Gal) proteins in each group are shown in Figure 28. Muscle levels of myostatin (differentiation inhibitor) and SA- $\beta$ -Gal (senescence) were increased in the older group, while those of follistatin, MyoD and myogenin decreased, suggesting an age-related loss of muscle growth and differentiation potential. These data defined a profile of age-related changes in muscle regulatory proteins and informed the selection of muscle protein outcome measures to be used in the second part of the study: (-)-epicatechin treatment of middle aged subjects.

In part 2, a small pilot treatment study was performed in human subjects ( $n=6$ , average age  $41 \pm 5$  years) to assess the effects of (-)-epicatechin on muscle strength and blood levels of myostatin and follistatin. Subjects were treated for 7 days with 25 mg of (-)-epicatechin in capsules BID. Muscle strength was assessed by hand grip dynamometry (thrice with each hand, alternating hands between trials and resting for 10 seconds in order to prevent fatigue, maximum strength attained was used for analysis). Myostatin and follistatin was measured in blood samples taken before and after the 7 days of treatment. Treatment resulted in a bilateral increase in hand strength of  $\sim 7\%$  which was accompanied by a significant increase in the ratio follistatin/myostatin (Figure 29). This coupling of functional and molecular changes suggests that (-)-epicatechin has potential as a therapy to reduce progressive muscle loss.

Figure 28: Age-related muscle protein changes in human skeletal muscle samples.

[figure not shown]
[figure not shown]

Figure 29: Changes in muscle strength and follistatin/myostatin ratio following 7 day of (-)-epicatechin treatment.

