##### Participant Inclusion Criteria

- Male
- Age 18 years to 60 years
- Average to low daily physical activity
- Ability to ambulate for 75 meters without assistive devices
- Diagnosis of BMD confirmed by at least one the following:
  - Dystrophin immunofluorescence and/or immunoblot showing partial dystrophin deficiency, and clinical picture consistent with typical BMD, or
  - Gene deletions test positive (missing one or more exons) of the dystrophin gene, where reading frame can be predicted as 'in-frame', and clinical picture consistent with typical BMD, or
  - Complete dystrophin gene sequencing showing an alteration (point mutation, duplication, or other mutation resulting in a stop codon mutation) that can be definitely associated with BMD, with a typical clinical picture of BMD, or
  - Positive family history of BMD confirmed by one of the criteria listed above in a sibling or maternal uncle, and clinical picture typical of BMD.
- Nutritional, herbal and antioxidant supplements taken with the intent of maintaining or improving skeletal muscle strength or functional mobility have been discontinued at least 2 weeks prior to screening (daily multivitamin use is acceptable).
- Hematology profile within normal range
- Baseline laboratory safety chemistry profile within normal range
- No plan to change exercise regimen during study participation

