## 6.3 Treatment of Participants

### 6.3.1 Epicatechin Administration

Participants will receive epicatechin by mouth 50mg twice per day (100mg per day total dose). Study medication will be supplied as a clear 25mg (#3) gelatin capsule without any inert fillers. Participants will take two capsules in the morning at approximately 7:30AM at least 15 minutes before the morning meal and two with the evening at approximately 7:30PM at least 1 hour after the evening meal as absorption is limited by some milk products.

For details on participant enrollment and randomization, please refer to the study procedures chart (Table 3) and pharmacy sections. When medications have been received, they should be dispensed to participants from their assigned investigational drug supply along with the medication instructions handout for parents and physicians.

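### Dietary cocoa, chocolate and tea are neither restricted nor recorded, so a change in intake could not be told apart from a drug effect, and cocoa eaten near sampling can affect the PK levels

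*Combined protocol and SAP*

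**What the plan says.** **Dose and design.** Section 6.3.1: "Participants will receive epicatechin by mouth 50mg twice per day (100mg per day total dose"). The morning dose is taken at least 15 minutes before breakfast. Section 1.3 describes one open-label arm of 10 adults, and Aim 1 in Section 1.4 compares biopsies with the pre-treatment baseline.

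**Food as a source.** Section 1.1 states that a commercial 60% cocoa chocolate "will provide 0.84 mg/gram of (-)-epicatechin and 10.6 mg/gram of total flavanols". Figure 3 gives a second figure, a plasma profile "after ingestion of 100g of dark chocolate (79 mg (-)-epicatechin"). The text after Table 2 treats oral doses from 25 mg upward as pharmacologically relevant and reports that "an intake of 25 mg (-)-epicatechin per day was associated with significant reductions in SBP and DBP".

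**What is controlled.** The inclusion criteria require that "Nutritional, herbal and antioxidant supplements taken with the intent of maintaining or improving skeletal muscle strength or functional mobility have been discontinued" at least two weeks before screening. Section 6.3.4 limits new medications. Table 3 schedules a review of medications and dietary supplements at screening, Day 1, Weeks 4 and 8 and early withdrawal. Week 2 is left out, although Section 8.1 samples PK then. None of these places mentions foods, and no diet record is scheduled.

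**The concern.** The protocol's own human muscle evidence comes largely from food. In Section 5.1, biopsy changes in PGC1a, nNOS, follistatin, myogenin and MyoD followed a cocoa beverage and chocolate. Aim 1 names the same markers under the primary endpoint. The plan therefore assumes that cocoa can move the quantities it will measure, yet leaves cocoa intake free and unobserved.

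Two results are exposed. The first is the pre/post change. Participants know they are taking a compound found in chocolate and tea. If intake rises after enrolment, the change may be inflated; if it falls, the change may be reduced; if it is high and stable, the contrast may be diluted. No control group would share the shift. Section 11 judges success by whether a response magnitude would give sufficient power in a 30-person Phase IIB study, so an unrecognised error would carry into that decision.

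The second is the PK profile. Section 8.1 measures epicatechin metabolites, which chocolate also produces, so a sample cannot show which source they came from. Aim 3 compares these profiles with the literature.

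**Working it through.** **Inputs.** Chocolate content: 0.84 mg/g (Section 1.1) and 79 mg per 100 g = 0.79 mg/g (Figure 3). Dose: 50 mg twice daily. Half-life: about 2-2.5 h (Section 3.1). Peak level: Section 3.1 says that oral bioavailability "for (-)-epicatechin in cocoa/chocolate is ~10-20 nM/mg ingested". Portion sizes below 100 g are my assumptions; the documents define none.

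**1. Reproduce the plan's figures.** Table 2, column "Peak (-)-Epicatechin Exposure (nM/mg"), dark chocolate row: 873/79 = 11.05, stated 11.1. Six of the seven rows agree to rounding; the 135 mg cocoa drink gives 1245/135 = 9.22 against 9.3, about 1% off. The table's range is 7.2 to 21.7 nM/mg.

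**2. Content by portion** (grams x 0.79 to 0.84):

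| Dark chocolate | Epicatechin | Share of 100 mg/day |
|---|---|---|
| 25 g | 20-21 mg | 20-21% |
| 30 g | 24-25 mg | 24-25% |
| 40 g | 32-34 mg | 32-34% |
| 50 g | 40-42 mg | 40-42% |
| 100 g | 79-84 mg | 79-84% |

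In reverse: 25 mg needs 25/0.84 = 29.8 g to 25/0.79 = 31.6 g. 50 mg needs 50/0.84 = 59.5 g to 50/0.79 = 63.3 g.

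**3. PK on a sampling day.** Assume 40 g at breakfast, soon after the dose, with coinciding peaks and the same nM/mg for food and capsule.
- Chocolate: 40 x 0.84 = 33.6 mg; 33.6 x 10 to 20 = 336-672 nM.
- Capsules: 50 x 10 to 20 = 500-1000 nM.
- Ratio: 33.6/50 = 67%, whatever common nM/mg is used.
- At the Table 2 extremes: chocolate 33.6 x 7.2 = 242 to 33.6 x 21.7 = 729 nM; capsules 50 x 7.2 = 360 to 50 x 21.7 = 1085 nM.

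**4. How long food matters.** Remaining fraction = 0.5^(t/half-life), for half-lives of 2 and 2.5 h:
- 8 h: 6.3-10.9%
- 12 h: 1.6-3.6%

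Even 84 mg eaten 12 h before sampling (10 h after its peak) leaves (84/50) x 0.5^(10/2) = 5% to (84/50) x 0.5^(10/2.5) = 10.5% of the peak from a 50 mg dose. Material PK interference therefore needs intake within roughly 8 h of the sample.

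**5. Dose-reduction trigger.** A 50 mg dose plus 100 g of chocolate at the same time is 50 + 84 = 134 mg, so 134 x 10 to 20 = 1340-2680 nM (about 1.3-2.7 uM), or 134 x 21.7 = 2908 nM at the top Table 2 ratio. Section 6.3.2 sets the trigger at 4 umol/ml, which is 4,000,000 nM. Even 4000 nM would not be reached.

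**The case against.** **Stable intake cancels.** Habitual chocolate is present before and after treatment, and Section 5.3.3 describes exposure as roughly dose-proportional. Constant intake therefore adds no direct shift to the difference. This stands: bias in the change mainly needs intake to move, and the documents contain no evidence that it will.

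**Milligrams from food are not shown to equal milligrams of drug for muscle.** The grip result in Section 5.2 came from purified capsules in six healthy volunteers ("Subjects were treated for 7 days with 25 mg of (-)-epicatechin in capsules BID"); the 25 mg/day figure concerns blood pressure; and Section 1.1 says catechin antagonises epicatechin. This also stands as a limit on size. It does not remove the point, because Section 5.1 reports muscle changes after cocoa itself, although its text gives no daily epicatechin amount.

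**PK is partly protected.** The half-life is short, the morning dose comes before breakfast, and the lipid profile in Section 9.1 is fasting, so the pre-dose draw is plausibly fasted. That helps the trough. It does not cover the 2 h and 4 h samples, because breakfast may follow the dose by 15 minutes and the peak comes at about 2 h.

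**Stronger readings that fail.** A reader might infer that ordinary servings supply 50-84 mg. The documents define no serving: 50 mg needs about 60 g, and the 100 g is a test meal in a cited study. A reader might extend the figures to tea, but only amounts for tea extract or a catechin mixture are given, never content per cup. A reader might fear that diet could trigger the dose reduction in Section 6.3.2; step 5 shows it could not.

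**Conclusion.** The gap is real: food sources of the study compound are neither limited nor logged, and by the protocol's own figures they can be a material share of the dose. About 30 g of dark chocolate matches the lowest daily amount the protocol calls relevant; 100 g is about four fifths of the daily study dose. In this design a diet change could not be distinguished from treatment, or looked for afterwards.

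The finding is that diet can affect the results, not that it has contaminated them. Size and direction are unknown because no intake data are given. The 67% PK addition rests on an assumed 40 g portion, coinciding peaks and equal exposure per mg from food and capsule; it vanishes if no cocoa is eaten in the hours before a sample. For tea, only the lack of restriction and recording can be claimed. This is a worthwhile improvement to the plan, not a flaw that invalidates it.

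**What to change.** - In Sections 6.1.1 and 6.3.4, ask participants to keep habitual cocoa, chocolate and tea intake unchanged from screening to Week 8.
- In the same places, ask them to take none from the evening before the Baseline, Week 2, Week 4 and Week 8 visits until the last PK sample. Step 4 supports an evening cut-off: after 12 h only 1.6-3.6% remains.
- Add one line on intake of these foods to the medication and supplement form, and schedule that form at Week 2 in Table 3, where PK is sampled but the form is missing.

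The cost is one instruction, one form line and one extra form per participant, with a small participant burden. No endpoint or sample size changes. Stable intake does not undo dilution from a high baseline intake, but the record would at least make that visible and allow change to be described against reported diet.

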**Table 2: Selected human oral bioavailability studies of (-)-epicatechin**

Reference	Test Article	(-)-Epicatechin (mg)	Peak (-)-Epicatechin Species in Plasma (nM)	Peak (-)-Epicatechin Exposure (nM/mg)
Loke, W.M., et al., 2008 [52]	(-)-Epicatechin	200	3570	17.85
Ottaviani, J.I., et al., 2011 [18]	(-)-epicatechin added to cocoa vehicle	125 (mean)	~900	~7.2
Ottaviani, J.I., et al., 2012 [19]	Cocoa drink	135 (mean)	1245	9.3
Actis-Goretta, L., et al., 2012 [47]	Dark Chocolate	79	873	11.1
Donovan, J.L., et al., 2006 [53]	Cocoa drink	55	630	11.5
Schroeter, H., et al., 2006 [11]	Cocoa flavanols: 917 mg	174	~1950	~11.2
Baba, S., et al., 2000 [15]	Dark chocolate	220	4770	21.7

Oral doses of (-)-epicatechin between 25 and 200 mg have been shown to be pharmacologically relevant. A 200 mg oral dose increased measures of plasma NO and decreased the vasoconstrictor endothelin-1 [52], while administration of an ~75 mg dose (1 mg/kg body weight) resulted in significant improvement in vascular function (FMD) [11]. A recent meta-analysis of clinical data reported that an intake of 25 mg (-)-epicatechin per day was associated with significant reductions in SBP and DBP [54].

#### 4 PRELIMINARY STUDIES

[figure not shown]
##### 4.1 Preclinical Data

Collaborators of Cardero Therapeutics at the University of California, San Diego (UCSD) have conducted cell culture and animal studies examining the ability of (-)-epicatechin to induce mitochondrial biogenesis and SkM protein synthesis, resulting in improved muscle structure and function.

[figure not shown]
##### 4.1.1 (-)-Epicatechin Increases Mitochondrial Respiration and Biogenesis in Cultured Human Skeletal Muscle Cells (unpublished data)

The effect of (-)-epicatechin on mitochondrial respiration, biogenesis and structure in human skeletal muscle cells *in vitro* was examined. Human skeletal muscle cells from a healthy subject were treated with 0.1  $\mu$ M of (-)-epicatechin (in cell culture) for 48 hours. The treated muscle cells manifested a markedly enhanced capacity for oxidative phosphorylation (Figure 4). The ability of epicatechin to stimulate the capacity for oxidative phosphorylation in human muscle fibers treated with epicatechin allows the muscle cell to substantially increase its rate of oxidative phosphorylation in response to the metabolic demand placed on the cells by FCCP, which decreases the mitochondrial membrane potential. Importantly for safety reasons, neither endogenous nor resting oxidative phosphorylation in muscle cells is affected.

**Figure 4: (-)-Epicatechin enhances mitochondrial respiration**

Treated cells were then examined using electron microscopy (Fig 5). The electron micrographs illustrate two effects. One is the marked increase in mitochondrial number. Even more unusual is the increased number of cristae per mitochondrion, suggestive of the potential for increased ATP synthesis per mitochondrion. To our knowledge, cristae density within a mitochondrion has not previously been demonstrated to be acutely modulatable before. Mitochondrial biogenesis can also be blunted by the use of eNOS inhibitors, supporting a role for the NO system in the mechanism of action for (-)-epicatechin's effects.

[figure not shown]
**Figure 5: (-)-Epicatechin increases mitochondrial number and cristae density in human skeletal muscle cells (unpublished data)**

Electron microscopy of human skeletal muscle cells from healthy human subjects treated with 0.1  $\mu$ M of (-)-epicatechin (in cell culture) for 48 hours are shown in panels C and D; cells from the same subject without treatment are shown in A and B. Based on blinded independent analysis of cristae/mitochondrial membrane ratio the (-)-epicatechin treated cells ( $1.33 \pm 0.34$  vs. control  $0.88 \pm 0.49$ ) had statistically significant ( $p=0.03$ ) more cristae membrane where the oxphos complexes are located, suggesting (-)-epicatechin-treated cells have a greater capability for ATP generation. In addition to increases in cristae membrane, treated cells also had an increased number of mitochondria.

#### 4.1.2 (-)-Epicatechin Induces Mitochondrial Biogenesis Pathway in Human Coronary Artery Endothelial Cells (unpublished data)

[figure not shown]
Recent unpublished experiments established that (-)-epicatechin initiates mitochondrial replication via the activation of two co-factors that participate in the classical transcription pathway for mitochondrial biogenesis: The Estrogen Related Receptor (ERR) pathway and the activation of PGC1 $\alpha$ . The ERR pathway comprises an orphan nuclear receptor complex consisting of 3 subunits,  $\alpha$ ,  $\beta$  and  $\gamma$ . When exposed to the unknown ligand, they trimerize in the cytoplasm and form a complex with PGC1 $\alpha$ , and subsequently localize to the nucleus, where they initiate the transcription pathway for mitochondrial biogenesis [55]. Nuclear localization of the  $\alpha$  subunit is accepted as an indicator of ERR activation. Human coronary artery endothelial cells (HCAEC) exposed to (-)-epicatechin demonstrated localization of ERR $\alpha$  to the nucleus within 30 minutes (Fig 6).

**Figure 6: (-)-Epicatechin induces estrogen-related receptor alpha translocation (activation) into the nucleus of HCAEC**

[figure not shown]
#### 4.1.3 (-)-Epicatechin Induces Expression of Mitochondrial Biogenesis Factor PGC-1 $\alpha$ in Aged Mice (unpublished data)

The peroxisome proliferator-activated receptor gamma (PPAR $\gamma$ ) coactivator-1 $\alpha$  (PGC-1 $\alpha$ ) is a transcriptional coactivator of nuclear receptors and other transcriptional factors that can enhance multiple aspects of cellular energy metabolism, including mitochondrial biogenesis and angiogenesis [56, 57]. Expression of PGC-1 $\alpha$  in cultured mammalian cells or specific tissues of transgenic mice increases number and mass of mitochondria together with a strong enhancement of cellular respiratory capacity [58], suggesting that PGC-1 $\alpha$  would be expected to enhance mitochondrial biogenesis and promote muscle repair and regeneration. The effects of (-)-epicatechin on PGC-1 $\alpha$  levels were examined in young (6 mo), and old (26 mo) mice. Senile mice treated with epicatechin for two weeks exhibited increased expression of PGC-1 $\alpha$  across all tissues evaluated (Fig 7A). These animals also demonstrated correlative mitochondrial biogenesis (not shown). When PGC-1 $\alpha$  level of expression was compared in the senile mice to young mice, they were markedly diminished, and stimulated by epicatechin treatment in as little as two weeks (Fig 7B).

